Title: A Feasibility Study to Determine the Effects of a Novel Mattress Support for Treatment of Positional Obstructive Sleep Apnea at Home

Principal Investigators:

[name] M.D. (IRB contact PI)
Professor of Medicine and Neuroscience
[name]
[name]
[name]
[contact]
[contact]
E-mail: [contact]

Co-investigators:

[name]
Assistant Professor of Medicine and Neurology
Department of Neurology
[name]
[name]
[contact]
[contact]
Email: [contact]

[name]
Center for Biostatistics
The Ohio State University
College of Medicine Department of Biomedical Informatics
[name]
[contact] Office
[contact]

Key Personnel:

[name]
[name]
[name]
[name]
[contact]

Additional contacts:

[name]
Clinical Trials Management Office
College of Medicine
The Ohio State University

[contact]

[name]
Clinical Trials Management Office
College of Medicine
The Ohio State University
[contact]

[name]
Clinical Trials Management Office
College of Medicine
The Ohio State University
[contact]

[name]
Clinical Trials Management Office
College of Medicine
The Ohio State University
[contact]

Performance Sites:
The Ohio State University Wexner Medical Center

IND number:
Not applicable

IDE: non-significant risk (NSR) investigational device that meets the abbreviated Investigational Device Exemptions (IDE) requirements at 21 CFR 812.2(b)

SPONSORING ORGANIZATION: Hill-Rom Co., Inc.

I. Objectives

- 1) Determine the effects of a mattress support (Wave 4.3) that promotes the avoidance of supine airway position at home on the apnea-hypopnea index (AHI) in patients with positional obstructive sleep apnea (OSA).
- 2) Determine the effects of Wave 4.3 on subjective measures of sleepiness and daytime function in patients with positional OSA.
- 3) Determine the effects of Wave 4.3 on subjective measures of sleep quality in patients with positional OSA.

The risks associated with this study are minimal compared to the potential benefits. Knowledge about the effects of a simple mattress support that promotes the avoidance of supine position at home would be an important advance in the care of these patients, since currently established treatments such as continuous positive airway pressure (CPAP) and mandibular advancement device (MAD) have limitations in terms of treatment adherence.

II. Background and Rationale

Obstructive sleep apnea (OSA) is a major public health problem that affects millions of Americans.¹ The condition is characterized by repetitive upper airway obstructions during sleep causing oxyhemoglobin desaturations, hypercapnia, arousals and increases in sympathetic tone.² OSA causes daytime sleepiness and impairs daytime function.³⁻⁵ OSA is associated with a variety of adverse health, economic, and safety consequences that includes hypertension, stroke, cardiovascular disease, diabetes, motor vehicle crashes, reduced work performance, and increased healthcare utilization.⁶⁻¹¹ The first line treatment for OSA is CPAP.¹² However, patient adherence to CPAP is a major problem. An estimated 50% of patients do not use the device at least 4 hours per night (the recommended minimum hours of nightly use).¹³ Mandibular advance devices (MAD) are also utilized for OSA treatment, but this form of therapy is limited by patient suitability, adherence, and efficacy.¹⁴ Therefore, alternative treatments are needed in the treatment of OSA.

As an alternative to CPAP and MAD, patients with positional obstructive sleep apnea (POSA) may be candidates for therapies that are designed to prevent the supine posture during sleep, ie, positional therapy.¹⁵ POSA is said to be present when there is a reduction in the AHI during non-supine sleep compared to supine sleep.¹⁶ Approximately 30% of patients referred to sleep medicine clinic have positional OSA.¹⁷ We, and others, have shown that positional OSA is very common in those with mild to moderate disease as defined by an AHI < 30 events/hr based on polysomnography (PSG).^{16,17} Frank and colleagues proposed a new classification system for individuals with POSA called the Amsterdam Positional OSA Classification (APOC) in an attempt to have a universal definition of the condition.^{18,19} POSA include patients who have a total AHI >5/hr and spend >10% time in the supine and non-supine positions, and are classified as: APOC I if the AHI is <5/hr in the nonsupine position, APOC II if the total AHI is 5-40/hr and the non-supine AHI is reduced by 50% but remains >5/hr, and APOC III if the total AHI is >40/hr and the non-supine AHI is reduced by 25-50%.¹⁸

Currently, there are several strategies that are used to avoid the supine position during sleep. These include simple instructions to avoid the supine position, use of tennis ball sewn on a pajama top, and devices that are worn during sleep that vibrates whenever the supine posture is detected.^{15,20-22} These techniques are limited by poor compliance (tennis ball technique), concerns about sleep disruption due to the vibrations, and absence of long-term efficacy data.^{20,21,23} Therefore, investigation of other treatment options is needed for the treatment of POSA.

Wave 4.3 is a novel device that has been developed by the Hill-Rom Early Innovation team (Hill-Rom, Batesville, IN) for treatment of OSA that occurs in the supine position. The investigational device in the proposed study is a non-significant risk (NSR) device that is designed to be used as a mattress support at home and with any combinations of sleep pillows, bed linens, and bed clothes. Hill-Rom performed initial testing on this device, and Hill-Rom's Executive Director of Medical Safety believes this device poses minimal to no risk to patient safety.

III. Procedures

A. Research Design

This is a feasibility study of sleeping at home with and without the novel mattress support (Wave 4.3) for two consecutive weeks in patients with POSA. Informed consent will be obtained from all participants.

B. Subject Selection:

1. *Inclusion/Exclusion Criteria*

A. Key Inclusion Criteria

We will recruit subjects who are:

- 18-75 years of age
- Willing and able to give informed consent
- Able to speak and understand English
- Previous sleep study prior to enrollment done based on previous clinical evaluation by the subject's treating physician in the course of usual clinical care:
 - a. overall AHI 5-40 events/hr.
 - b. at least 10% time spent in the supine and 10% time in the non-supine positions.
 - c. APOC I and APOC II
 - d. central respiratory events < 50% of the total number of apneas and hypopneas
- Using at least a queen-sized mattress when sleeping at home
- Patients who meet the above criteria who have been prescribed CPAP or dental device but are non-adherent to treatment will be enrolled in the study. CPAP non-adherence will be defined as average nightly use < 4hrs/night

based on a download of the CPAP machine, or self- acknowledged discontinuation or non-regular of CPAP use.

- Patients who meet the above criteria who have been prescribed CPAP or dental device but are adherent to treatment will be enrolled in the study provided that: a) they are willing to use the Wave device instead of their CPAP or dental device for the duration of the study, and b) they do not have severe OSA defined as an AHI > 30 events/hr in their clinical sleep study.

B. Key Exclusion Criteria

- Incapable of giving informed consent
- Under the age of 18
- Active titration of medication
- Pregnancy, lactation (will be screened with urine pregnancy test)
- Self-reported Substance abuse (current)
- Excessive alcohol consumption
 - Excessive alcohol use is defined as:
 - More than 3 glasses of wine a day
 - More than 3 beers a day
 - More than 60 mL of hard liquor a day
- Use of home oxygen
- Presence of severe daytime sleepiness defined as an Epworth sleepiness scale score ≥ 16 or a prior history of falling asleep while driving
- Presence of cardiac pacemaker or automatic implantable cardioverter-defibrillator (AICD).
- Unstable medical problem such as uncontrolled hypertension.
- Body Mass Index (BMI) $>45 \text{ kg/m}^2$
- Any other clinically significant condition that, in the opinion of the investigators, might put the subject at risk of harm during the study or might adversely affect the interpretation of the study data.

2. Screening Procedures

A screening visit will be scheduled to determine eligibility. A separate informed consent for the purpose of screening potential candidates will be obtained. Female patients of childbearing potential will be required to have a negative pregnancy test result at screening.

After their study participation has ended, those with an AHI ≥ 5 /hour based on the HSAT will be referred to their primary care physician or the sleep medicine clinic for treatment discussion using established therapies

3. Vulnerable Populations

- Children, fetuses, neonates, or prisoners are not included in this research study.

4. Populations vulnerable to undue influence or coercion

Cognitively impaired persons are not included in this research study, since the potential subject has to be able to give informed consent. Should an OSU employee or student be approached, they will be given the opportunity and time to consider participation and will be reassured that declining to participate will not jeopardize or hinder their standard of care at the OSU Sleep Disorders Center, nor will it have any bearing on either their student status or employment.

5. *Inclusion of Women and Minorities*

Both men and women of all races and ethnic groups are eligible for this study.

C. Study Plan

This is a preliminary single-arm study. The study will last up to 4 weeks including the screening period. Subjects will sleep using the mattress support at home for two consecutive weeks.

Outcome measures will include: AHI derived from HSAT (primary outcome), oxygen desaturation index (ODI), Epworth Sleepiness Scale (ESS) score, Functional Outcomes of Sleep Questionnaire (FOSQ), Visual Analog Scale (VAS) and questionnaire assessments of sleep quality, and actigraphic sleep measures. Subjects will also keep a sleep diary every night for the duration of the study. Subjects will be asked about their bed partners' report on snoring and witnessed apneas.

Visit 1: Screening Visit and Procedures

A separate informed consent for the purpose of screening potential candidates will be obtained.

Instead of an in-person visit, the participant consent for the purpose of screening will be conducted using a REDCap-based electronic consent form for those who are willing and able to do this. The consent form will be developed in REDCap, a secure, web-based, HIPAA-compliant, data collection platform with a user management system allowing project owners to grant and control varying levels of access to data collection instruments and data (e.g. read only, de-identified-only data views) for other users. Potential participants will participate in the consent process by:

- Being approached in-person at The Ohio State University and accessing the REDCap survey via iPad or other portable electronic device and/or
- Self-initiated access of consent forms on personal portable electronic devices using posted QR codes or web-links on study posters, brochures, or websites. Self-initiated accessing of consent forms may occur at The Ohio State University campus or at home.
- Participant signatures will be obtained using a typed name. Upon completion of the consent encounter, participants will be provided with a copy of the consent document by printing a pdf copy of the consent form.
- During the in-person consent process, consent will be obtained by a member of the study team. For self-initiated consent, contact information will be provided (email and phone) for prospective participants to contact a member of the study team with questions, prior to consent.

- After the screening consent has been signed, female patients of childbearing potential will be required to have a negative pregnancy test result.
- During this visit, the following will also be obtained:
 - a. Sleep Questionnaire and Medical History
 - b. Medication list
 - c. Body Mass Index, neck circumference (NC), blood pressure (BP), resting pulse oximetry, pulse rate
 - d. Collect results of the previous clinical sleep study
 - e. CPAP adherence, if applicable
 - f. Epworth Sleepiness Scale (ESS) score
 - g. Instructions on how to use the HSAT equipment at home for one night to obtain the baseline research HSAT study. Those with technically inadequate HSAT will have the study repeated.
- The following are the reasons why subjects may not proceed with the study after screening:
 - a) No POSA or POSA with APOC III based on the previous clinical sleep study.
 - b) No POSA or POSA with APOC III based on the baseline research HSAT study.
 - c) Meets one of the exclusion criteria.
 - d) Does not meet inclusion criteria.
- **Expected visit length: 60 minutes**
- Participants will be requested to return the HSAT device either in-person or via mail in a pre-paid envelope.

Visit 2

- Those who remain eligible will then sign a separate informed consent for the remainder of the study. REDCap will not be used for the consent process to the main study. The following will be obtained during this visit:
 - a. FOSQ
 - b. Assessment of sleep quality: VAS and Questionnaire
 - c. Actigraphy for duration of the study
 - d. Medications changes
- Participants will be given instructions on how to use Wave 4.3 mattress support at home and a phone number to call for the research coordinator for questions. The mattress support will be delivered at the subject's home by professional staff of the sponsor (Hill-Rom) in the presence of the research coordinator or investigator.
- **Expected visit length: 30 minutes**

Visit 3.

- This will occur on the 14th day of sleeping with the mattress support (that is, after night 13). The purpose of this visit is to provide the HSAT device to be used while sleeping with the mattress support.
- Medication changes
- **Expected visit length: 20 minutes**

Visit 4.

- Return HSAT equipment.
- The following will be obtained during this visit:
 - a. ESS
 - b. FOSQ
 - c. Assessment of sleep quality: VAS and Questionnaire
 - d. Medication changes
- **Expected visit length: 30 minutes**
- It may be necessary to repeat the home sleep study for another night if data after sleeping with the Wave mattress support is not adequate.

Phone Calls: Phone calls will be made by an investigator or research staff to answer any questions that participants may have (will occur between Visits 2 and 3): after the second night (third day) and seventh night of sleeping on the Wave 4.3 surface.

Mattress support pick-up: The mattress support will be picked up by professional staff of the sponsor (Hill-Rom) in the presence of the research coordinator or investigator at a mutually agreed time.

Visit Schedule

Procedures	Visit #			
	1	2	3	4
Screening consent		x		
Study consent			x	
Pregnancy test, if applicable		x		
Clinical Sleep Study Results*	x			
CPAP adherence, if applicable	x			
Sleep Questionnaire and Medical History	x			
Medication list	x			
Medication changes		x	x	x
Height and weight	x			
Neck Circumference	x			
BP, Pulse rate, SpO ₂	x			
Provide HSAT Equipment	x	x		
ESS	x		x	
FOSQ	x	x		

Sleep quality	X	X
Wave instructions	X	
Actigraphy**	X	X X
Sleep diary**	X	X X

BP= blood pressure

SpO₂= oxygen saturation by pulse oximetry

HSAT= home sleep apnea test

ESS= Epworth Sleepiness Scale

FOSQ= Functional Outcomes of Sleep Questionnaire

VAS= Visual Analog Scale

*Clinical sleep study is completed per standard clinical care.

** Done while sleeping with Wave Mattress support for 14 days

D. Detailed Procedures

1. Clinical Sleep Study:

Subjects will undergo diagnostic sleep study according to the evaluation of their physician. This is the sleep study performed within the context of usual clinical care that will determine whether subjects meet the criteria for POSA.

2. OSU Sleep Questionnaire and Medical History (15 minutes)

Sleep Questionnaire (Visit 1 only; No need to complete if previously completed the OSU Sleep Disorders Center Questionnaire in sleep clinic)

3. Medication List (5 minutes)

For all subjects we will obtain information about medications they are currently taking, including supplements.

4. BMI, neck circumference, blood pressure, pulse rate, SpO₂ (10 minutes)

Blood Pressure, weight and height measurements (to calculate BMI) will be done during visit 1. We measure the neck circumference at a point just below the larynx (Adam's Apple) and perpendicular to the long axis of the neck. Blood pressure measurement will be done according to the usual standard protocol.

5. CPAP treatment adherence (5 minutes)

CPAP adherence will be obtained from the medical record or downloaded from the subject's machine if they are on CPAP therapy but will not be performed if they self- acknowledged discontinuation or non-regular of CPAP use.

6. Questionnaires (15 minutes)

- a. Epworth Sleepiness Scale (ESS) score
- b. Functional Outcomes of Sleep Questionnaire (FOSQ)
- c. Assessment of sleep quality: VAS and Questionnaire

7. Actigraphy

This device is the size of a small wristwatch that measures activity and is a non-invasive method of monitoring human rest/activity cycle. The instructions for the

device use will be provided. The data is then downloaded into a computer. A sleep diary is routinely administered with actigraphy.

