The primary endpoint for the study is the change in the AHI from baseline to the 14th night of sleeping with the surface. From prior data, we estimate the standard deviation of the paired differences to be 11.4. Using a one-sided paired t-test with type I error rate of 0.05, we will have 80% power to detect a 6 point reduction in AHI with 24 evaluable patients. We assume a loss to follow-up rate of 20% and a screen failure rate of another 20%; thus will enroll 40 patients.

Statistical methods

The primary analysis will assess the change in AHI from baseline to the 14th night of sleeping on the surface. We will use a one-sided paired t-test to assess the reduction in AHI. If the study is not stopped early for either efficacy or futility, the final analysis will conclude a significant reduction in AHI if the p-value is less than 0.048. Secondary endpoints will be assessed similarly using paired t-tests or appropriate non-parametric tests for paired data. We may also explore longitudinal changes in actigraphy measures using mixed effects models.

Interim Analysis:

Interim analyses for efficacy and non-binding futility will be conducted when 50% of the evaluable patients have reached the primary endpoint after 14 days of using the device. That is, it will be conducted after 12 patients have an evaluable primary endpoint. The analysis will assess the primary endpoint using the error spending approach described by Lan and Demets.^{25,27} The study will be stopped early for efficacy if the p-value is less than 0.006 and stopped for futility if the p-value is greater than 0.37. If neither boundary is reached, the trial will not be stopped early and will enroll the full planned number of participants.

V. Event Reporting

(a) Adverse Events

The ICH Guideline for Good Clinical Practice E6(R1) defines an adverse event (AE) as:

Any untoward medical occurrence in a patient or clinical investigation subject administered a pharmaceutical product and which does not necessarily have a causal relationship with this treatment. An AE can therefore be any unfavorable and unintended sign (including an abnormal laboratory finding), symptom, or disease temporally associated with the use of a medicinal product, whether or not considered related to the medicinal product.

As this is a study that does not include a pharmaceutical product intervention, this definition would include AEs that occur as a result of protocol procedures and protocol treatment.

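### The only ESS planned before Wave use appears also to be the score that excludes patients at 16 or more; this selection alone tilts the ESS change slightly against the device, and an ESS at Visit 2 would remove it

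*Combined protocol and SAP*

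**What the plan says.** Section I, Objective 2 is to "Determine the effects of Wave 4.3 on subjective measures of sleepiness and daytime function in patients with positional OSA". Section III.C (Study Plan) lists ESS among the outcome measures.

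The Key Exclusion Criteria in Section III.B include "Presence of severe daytime sleepiness defined as an Epworth sleepiness scale score ≥ 16". No lower ESS limit is set.

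In Section III.C, Visit 1 is the screening visit, and its item f is "Epworth Sleepiness Scale (ESS) score". Among the reasons for not proceeding after screening is "Meets one of the exclusion criteria". Visit 2, the last visit before Wave use, collects FOSQ and "b. Assessment of sleep quality: VAS and Questionnaire", with actigraphy and medication changes, but no ESS. ESS returns at Visit 4, item a. The visit schedule table is garbled in the available text, but it carries two ESS marks, which fits one score before Wave and one after.

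Section III.C also says "This is a preliminary single-arm study". In Section IV (Statistical methods), "Secondary endpoints will be assessed similarly using paired t-tests or appropriate non-parametric tests for paired data". No sentence names the ESS baseline, and nothing there deals with regression to the mean in ESS.

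**The concern.** ESS varies from one completion to the next. If the score that excludes patients at 16 or more is also the baseline, patients who scored high by chance that day are removed and those who scored low by chance are kept. On a second completion the retained group's mean moves back up, even with nothing changed. With no control arm, that rise is subtracted from any true fall in ESS.

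At stake is the sleepiness half of Objective 2: the estimated improvement would be somewhat too small, and a real one somewhat easier to miss. FOSQ and sleep quality do not share the problem, because they are first taken at Visit 2 and play no part in entry. The primary AHI analysis does not use ESS.

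**Working it through.** **The plan's own figure.** Section IV gives SD of paired AHI differences 11.4, a 6-point reduction, one-sided 5%, and 80% power with 24 evaluable patients. Exact noncentral-t power at n = 24 is 0.804, so 24 reproduces. Enrolment follows as 24/(1 − 0.20 − 0.20) = 40. No such figures are given for ESS. I carry forward n = 24 and the 20% screen-failure allowance.

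**Assumed inputs (not in the documents).** ESS roughly normal in screened patients, SD 4.5 or 5; retest correlation r of 0.7 or 0.8; 5% or 10% of screened patients excluded on ESS. The 20% allowance must cover every reason for screen failure, including the baseline HSAT, so 5 to 10% for ESS alone is compatible with it but not derived from it. The one-sided 5% paired t-test reads the word similarly as carrying over from the primary test. The 2-point fall is illustrative.

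**Formulas.** Scores are whole numbers, so the cut is at 15.5. Let k = (15.5 − mean)/SD and λ = φ(k)/Φ(k).

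- Expected rise with no effect = (1 − r) × SD × λ.
- SD of change, Visit 1 baseline: √[(1 − r)² × SD² × (1 − kλ − λ²) + SD² × (1 − r²)].
- SD of change, Visit 2 baseline with all patients kept: SD × √[2(1 − r)].
- Error and power: noncentral t on 23 degrees of freedom. The mean fall is −rise (error) or 2 − rise (power) with the Visit 1 baseline, and 2 (power) with the Visit 2 baseline.

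**Numbers.** At 5% excluded, k = 1.645 and λ = 0.1031/0.95 = 0.109. At 10%, k = 1.282 and λ = 0.1755/0.90 = 0.195. Example: 10% excluded, SD 5, r 0.7 gives 0.3 × 5 × 0.195 = 0.29.

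| Excluded | SD | r | Rise | Error, Visit 1 | Power, Visit 2 | Power, Visit 1 | Loss (points) |
|---|---|---|---|---|---|---|---|
| 5% | 4.5 | 0.8 | 0.10 | 3.5% | 95.5% | 94.1% | 1 |
| 5% | 5 | 0.8 | 0.11 | 3.5% | 91.3% | 89.0% | 2 |
| 5% | 4.5 | 0.7 | 0.15 | 3.2% | 86.0% | 82.1% | 4 |
| 5% | 5 | 0.7 | 0.16 | 3.2% | 79.1% | 74.0% | 5 |
| 10% | 4.5 | 0.8 | 0.18 | 2.6% | 95.5% | 92.6% | 3 |
| 10% | 5 | 0.8 | 0.20 | 2.6% | 91.3% | 86.6% | 5 |
| 10% | 4.5 | 0.7 | 0.26 | 2.2% | 86.0% | 78.1% | 8 |
| 10% | 5 | 0.7 | 0.29 | 2.2% | 79.1% | 69.1% | 10 |

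Error with the Visit 2 baseline is the nominal 5%.

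**Check by simulation.** With whole-number scores limited to 0–24, mean 10, SD 5 and r 0.8 (13.6% excluded), the formula gives a rise of 0.25 and simulation 0.26. With a second score taken after selection as baseline, the simulated change is about 0.00.

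**Visit 2 scores of 16 or more.** Among patients who pass at Visit 1, the chance of scoring 16 or more at Visit 2 is about 3% to 6% over the table's settings, and 6% to 8% at mean 10, SD 5. If those patients are withdrawn, the new baseline is cut off as well: at mean 10, SD 5, r 0.7, about 0.28 of 0.39 points of drift remain, or 0.28/0.39 ≈ 70%.

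**The case against.** A reader might infer that ESS can be expected to rise overall if Wave does nothing, so that the Objective 2 sleepiness test is biased against the device. The documents do not support that. Participants know they are sleeping on the device and report ESS themselves, so expectation could lower scores without a true effect. Adherent CPAP or dental-device users may enter provided "they are willing to use the Wave device instead of their CPAP or dental device for the duration of the study", and giving up that treatment could raise scores. These forces cannot be netted from the documents; the upward direction belongs to the selection effect alone. That objection stands. It does not justify keeping the artefact, since the other forces act whichever baseline is used.

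A reader might also infer a much larger drift by assuming a sleepier population. A screened mean of 12 with SD 5 gives k = 3.5/5 = 0.7, so ESS alone would exclude 24.2%, more than the plan's whole 20% allowance. I do not rely on that setting.

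Three further points stand. The Visit 1 score's double role is inferred. The study is powered for AHI only, so no ESS power was promised. An error rate below 5% is conservative and cannot by itself create a false claim of benefit. Against these, the Visit 1 score is the only scheduled value that can serve as baseline, and a missed improvement is still a cost in a study that names sleepiness as an objective.

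**Conclusion.** The point holds as a small, avoidable bias in one secondary measure. On the natural reading of the schedule, selection on the baseline ESS adds about 0.1 to 0.3 points to the expected change on a 0–24 scale. A nominal 5% one-sided test then runs at about 2 to 3.5%, and power for a 2-point fall drops by roughly 1 to 10 percentage points. These sizes rest entirely on the assumed SD, retest correlation, share excluded and sidedness. The effect is negligible if few patients score near 16 or if ESS is highly repeatable. The sign is known for this component only. This is a worthwhile improvement and not a threat to the trial's main conclusion.

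**What to change.** Add ESS to the Visit 2 list and the visit schedule, completed with the FOSQ and sleep-quality forms before the first Wave night. State that the Visit 1 ESS is used for eligibility only. In Section IV, define the ESS change as Visit 4 minus Visit 2 in all patients who proceed, and state whether the test is one-sided.

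The cost is one short questionnaire at a visit that already collects two others, a schedule entry and a few words in the analysis section. It needs no extra visit or patients.

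The downside is that some Visit 2 scores, about 3 to 8% under moderate assumptions, will be 16 or more. The investigator must state in advance how these are handled; this review proposes no rule. If such patients are withdrawn, most of the drift returns, so their number should be reported with the ESS result. If no Visit 2 ESS is added, the limitation should be stated when the ESS change is reported.
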